### *Secondary Response Variables*

Secondary outcomes are described above (Outcome Measures) and will be analyzed in a similar manner as the primary response variables.

## **Study Implementation**

Subjects will be admitted to the Metabolic Research Unit in the NIH Clinical Center. They will remain as inpatients throughout the 19 day duration of the short-term study. Upon admission, they will undergo a history and physical examination, and baseline labs will be obtained. Labs used to assess subject eligibility in all subjects include electrolytes, BUN, creatinine, CBC, and a pregnancy test for female patients of reproductive potential. Baseline serum 25-hydroxyvitamin D levels will be obtained in all subjects. In subjects with 25-hydroxyvitamin D levels below 20 ng/mL, vitamin D supplementation will be provided. An EKG and echocardiogram will be performed to assess eligibility. Height, weight, blood pressure, resting pulse, temperature will be obtained.

### **Diet**

After baseline phenotyping, subjects will be placed on a metabolic diet with a fixed food quotient, consisting of 40% carbohydrates, 20% protein, and 40% fat. Subjects will be asked to consume all food at meals, and snacks (of similar macronutrient composition to meals) will be provided ad libitum. All food will be provided by the metabolic research kitchen. Uneaten food will be weighed, and daily food intake (total kcal and macronutrient content) will be calculated.

### **Medications**

#### ***Pre-study Medications***

With the exception of insulin (discussed below) subjects will continue their pre-admission medications throughout the study. This includes oral hypoglycemic agents, and other medications either related or unrelated to mutation of the insulin receptor or its complications.

#### ***Liothyronine (T3)***

T3 is the active form of thyroid hormone. Our rationale for choosing liothyronine (T3) over levothyroxine (T4) for this study is for two reasons. First, due to the short duration of the initial proof of principle study (two weeks), we would prefer to use a formulation of thyroid hormone with a short half-life that can be rapidly titrated. The half-life of liothyronine is a few hours, versus levothyroxine which is one week, thus allowing us to rapidly titrate the dose. Secondly, we prefer to use a formulation of thyroid hormone that will maximally stimulate BAT without the need for conversion from T4 to T3 by type 2 deiodinase. By using liothyronine as opposed to levothyroxine, we are able to study the direct effect of T3 on BAT, and are essentially eliminating an additional step.

Replacement doses of T3 to achieve euthyroidism in hypothyroid adults are approximately 0.57 mcg/kg/day. Stable plasma T3 levels can be achieved with q8 hour T3 dosing. In this study, the goal will be to achieve peak plasma T3 levels between 125% and 150% of the upper limit of normal (200 ng/dL in the NIH Clinical Center laboratory). The estimated T3 dose to achieve this level of plasma T3 is 2 times the replacement dose, or 1.14 mcg/kg/day. In a 50 kg individual, this equals 57 mcg. T3 is available in dosing increments of 5 mcg; thus doses will be rounded (lower dose will be used if calculated dose is 0 to <2.5 mcg above a dose divisible by 5; higher dose will be used if dose is 2.5 to <5 mcg above a dose divisible by 5). By comparison, T3 at doses of 150 mcg per day (~2.1 mcg/kg/day, or

approximately 4 times the replacement dose) was given to healthy, euthyroid adults for 2 weeks, raising plasma T3 levels from 125 to 507 ng/dL. This treatment was well tolerated, with an increase in heart rate from 65 to 78 beats per minute, and weight loss of 2 kg, and the development of “mild to moderate symptoms of enhanced appetite, nervousness, headache, or palpitations”. In a similar study, T3 at doses of 75 to 100 mcg per day (1.1 to 1.4 mcg/kg/day) was given to healthy, euthyroid adults for 2 weeks, raising plasma T3 levels from 110 to 350 (range, 190-520) ng/dL, with no reported adverse events.

The dose titration scheme for T3 is as follows:

- Day 1: 1x replacement (0.57 mcg/kg/day)
- Day 2: 1.5x replacement (0.855 mcg/kg/day)
- Days 3-14: 2x replacement (1.14 mcg/kg/day)

Plasma T3 peak (2-4 hours, with a goal of 3 hours, after morning dose) and trough (just before morning dose) levels will be measured on a daily basis for the first week, and every other day thereafter. If the T3 peak or trough exceeds targets below, the peak and trough will be repeated the following day (or the same day at the investigators’ discretion), and doses will be reduced if trough or peak levels exceed targets on both measurements.

- Target trough T3 = 150-250 ng/dL (25% above or below the upper limit of normal of 200 ng/dL)
- Target peak T3 = 250-300 ng/dL

In addition, if subjects meet one or more of the following clinical and biochemical criteria the dose will be reduced to avoid toxicity:

- Tachycardia, defined as heart rate consistently over 110 over a 24 hour period
- Symptomatic palpitations
- Anxiety or nervousness that are not tolerable to the patient
- Development of systolic hypertension (defined as >130 mmHg AND a  $\geq$  10 mmHg increase over baseline) for a 24 hour period)
- Chest pain
- Congestive heart failure
- Diarrhea that is distressing to patient
- Weight loss > 4 kg or >10% of body weight (whichever is smaller)
- Peak T3 > 350 ng/dL

After the conclusion of the 2 week T3 treatment, subjects with poorly controlled diabetes will continue long-term (6 month) management with T3, at the maximum dose tolerated during the inpatient study (up to 1.14 mcg/kg/day). Because key safety monitoring and dose titration occur during the 2 week study, subjects must participate in the 2 week study in order to proceed to the 6 month study. During the next 6 months, doses will be reduced if the following toxicity criteria are met:

- Symptoms of thyroid hormone excess that are intolerable to the subject are reported by the patient, or elicited on monthly telephone screening, including:
  - Symptomatic palpitations (sensation of racing heart)
  - Changes in sleep, mood or behavior, school/work performance
  - Tremulousness, anxiety, sweating, diarrhea, or heat intolerance.
- Signs of thyroid hormone excess are detected at the 3 month NIH follow-up visit, including:
  - Tachycardia, defined as heart rate consistently over 110 over a 24 hour period
  - Development of systolic hypertension (defined as >130 mmHg AND a  $\geq$  10 mmHg increase over baseline) for a 24 hour period)

- Weight loss > 4 kg or >10% of body weight (whichever is smaller), AND body mass index less than 25 kg/m^2 (adults) or less than the 50th centile (children). This will permit healthy or desirable weight loss in overweight subjects.
- Trough T3 or free T4 more than 50% above the upper limit of normal on monthly safety laboratory evaluation

Special consideration will be provided for females taking oral contraceptive pills, as levels of thyroid hormone may appear falsely elevated though the patients remains clinically euthyroid. These patients may require further increases in doses of T3 to achieve desired peak levels.

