| Food intake measurement       | X | X | X | X | X | X | X | X | X | X | X | X | X | X | X | X | X | X | X |
| BP & heart rate               | X | X | X | X | X | X | X | X | X | X | X | X | X | X | X | X | X | X | X |
| Body weight                   | X | X | X | X | X | X | X | X | X | X | X | X | X | X | X | X | X | X | X |
| Pregnancy test                | X |   |   |   |   |   |   |   |   |   |   |   |   |   |   | X |   |   |   |

Long-term study:

| Study Month                                     | 1 | 2 | 3 | 4 | 5 | 6 |
|--|----------|----------|----------|----------|----------|----------|
| Thyroid function (home labs)                           | X        | X        |          | X        | X        |          |
| Pregnancy test (females)                               | X        | X        | X        | X        | X        | X        |
| Telephone contact (safety)                             | X        | X        |          | X        | X        |          |
| NIH visit  |          |          | X        |          |          | X        |
| Pill count   |          |          | X        |          |          | X        |
| Fasting research blood tests                           |          |          | X        |          |          | X        |
| Thyroid function                                       |          |          | X        |          |          | X        |
| Vital signs (BP, heart rate, temperature, body weight) |          |          | X        |          |          | X        |
| Metabolic Chamber                                      |          |          |          |          |          | X        |
| DEXA (body composition)                                |          |          |          |          |          | X        |
| DEXA (bone density)                                    |          |          |          |          |          | X        |
| OGTT   |          |          |          |          |          | X        |
| PET-CT (age ≥ 18 years)                                |          |          |          |          |          | X        |
| Glucose & lipid turnover                               |          |          |          |          |          | X        |

|                            |  |  |  |  |  |   |
|----------------------------|--|--|--|--|--|---|
| Bedside glucose monitoring |  |  |  |  |  | X |
| Food intake measurement    |  |  |  |  |  | X |

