| Echocardiogram             |  |  |  |  |  | X |

During the 6 month follow up period, safety labs will be obtained on a monthly basis, either locally near the subject’s home or at NIH. Safety labs will consist of trough T3 level, free T4, TSH, and pregnancy test (females). Monthly telephone assessments will be conducted during the months that no NIH visit is scheduled. This will include review of compliance, as well as screening for symptoms of hyperthyroidism, including changes in sleep, mood or behavior, school/work performance, tremulousness, anxiety, sweating, diarrhea, heat intolerance, and patient self-measurement of pulse rate and weight.

For those subjects where it is not feasible (due to distance from the NIH or inconvenience) for them to return to the NIH for a 3 month follow-up visit, the research team will communicate with the subject’s primary doctor (or endocrinologist) and see if they are willing to evaluate them. The local physicians would not be engaged in human subject research because they would be providing medical services that would typically be performed as part of routine clinical monitoring. The physician would be requested to obtain the following labs: thyroid function tests, fasting glucose, insulin, c-peptide, lipid panel, free fatty acids and high-sensitivity C-reactive protein. Research samples for storage would not be obtained as it would be difficult to ensure consistency in processing. Additionally the clinic visit would include vital signs, weight and a conversation about their medication compliance. All results would need to be faxed to the research team at the NIH.

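### Tolerable chest pain at home does not by rule require a T3 dose reduction in the 6-month phase, although any chest pain does in the 2-week phase

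*Combined protocol and SAP*

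**What the plan says.** The protocol's section on liothyronine (T3) has two dose-reduction lists.

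For the 2-week inpatient study it says: "In addition, if subjects meet one or more of the following clinical and biochemical criteria the dose will be reduced to avoid toxicity". Nine criteria follow. Chest pain and congestive heart failure are among them, each without a qualifier. Other items in the same list do have one: anxiety must be beyond what the patient can tolerate, and diarrhea must cause distress.

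For the long-term phase a new list begins: "During the next 6 months, doses will be reduced if the following toxicity criteria are met". It contains:

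- a symptom criterion: "Symptoms of thyroid hormone excess that are intolerable to the subject are reported by the patient, or elicited on monthly telephone screening, including", followed by palpitations and a set of neuropsychiatric, sweating, bowel and heat symptoms;
- a sign criterion: "Signs of thyroid hormone excess are detected at the 3 month NIH follow-up visit, including", with tachycardia and systolic hypertension listed;
- weight loss, now with a body mass index condition, for which a reason is given: "This will permit healthy or desirable weight loss in overweight subjects";
- a limit on trough T3 or free T4 at the monthly laboratory check.

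Neither chest pain nor heart failure is named in this second list, and nothing says that the first list stays in force.

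Under Study Procedures, the telephone screen names hyperthyroid symptoms and self-measured pulse and weight. It does not name chest pain, breathlessness or swelling. A subject who cannot return at month 3 may be seen by a local physician, who is asked for laboratory tests, vital signs, weight and a discussion of compliance.

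**The concern.** Whether a dose of T3 should come down for chest pain ought not to depend on whether the patient can bear the pain. The 2-week list takes that view. The 6-month list does not, although in that phase the subject is at home and seen far less often. The Risks/Discomforts section itself associates long-term hyperthyroidism with a possible increase in cardiovascular events. A named cardiac trigger is therefore missing from the phase in which the protocol places that risk.

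What is at stake is patient safety in a small number of subjects: at least 7 are planned for the 6-month study, within an enrollment cap of 20. The glucose disposal and A1c analyses do not depend on this point.

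**Working it through.** The documents give no figure to reproduce. The check is a comparison of the two lists, followed by a search for any rule elsewhere that closes the gap.

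**Step 1: each 2-week criterion against the 6-month list.**

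| 2-week criterion | 6-month counterpart |
|---|---|
| Tachycardia | Named, same threshold, as a sign at the 3 month visit |
| Systolic hypertension | Named, same threshold, as a sign at the 3 month visit |
| Palpitations | Named, must now be intolerable |
| Anxiety or nervousness | Anxiety named, must be intolerable |
| Diarrhea | Named, must be intolerable |
| Weight loss | Kept, with a body mass index condition |
| Peak T3 above 350 ng/dL | Replaced by a limit on trough T3 or free T4 (50% over the upper limit of normal) |
| Chest pain | Not named |
| Congestive heart failure | Not named |

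That is 6 kept + 1 replaced + 2 not named = 9.

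**Step 2: apply the 6-month list to specific cases.**

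- *Tolerable chest pain reported by telephone.* The symptom list is open, so chest pain could be read in as a symptom of thyroid hormone excess. It then fails the intolerability condition. It does not meet the sign, weight or laboratory criteria by itself. No reduction is required. In hospital the same report requires one.
- *Intolerable chest pain.* This can be read in under the symptom criterion, so a reduction can be required. It does depend on attributing the pain to thyroid hormone excess, and Risks/Discomforts does not list chest pain among the expected hyperthyroid symptoms.
- *Heart failure found at the 3 month NIH visit.* The sign list is open and has no tolerability condition, so a reduction can already be required.
- *Heart failure found between visits or at a local month-3 visit.* The sign criterion refers to the NIH visit, so no trigger clearly applies.

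**Step 3: look for a rule elsewhere.** Risks/Discomforts ties reduction to intolerable symptoms or to the defined criteria, which leads back to the same list. The section on adverse events requires recording and reporting. Withdrawal Criteria lets the investigator withdraw a subject by judgement. None of these requires a dose reduction for chest pain.

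**Step 4: look at detection.** The EKG is scheduled at baseline only, and the echocardiogram is repeated only at month 6. Between visits, detection rests mainly on what subjects report, and neither chest pain nor breathlessness or swelling has a named question. Coverage of a local month 3 is also unclear: the text says "Monthly telephone assessments will be conducted during the months that no NIH visit is scheduled", which could include it, but the schedule marks calls at months 1, 2, 4 and 5 only.

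**The case against.** The best defense is that the lists differ because the settings differ. Part 1 is titration under close observation. Part 2 continues a dose already shown to be tolerated, and the protocol gives the reason: "Because key safety monitoring and dose titration occur during the 2 week study". Part 2 also has monthly hormone levels with a mandatory reduction above the limit. The tolerability condition is applied generally in Part 2, to palpitations as well, so chest pain was not singled out. Since chest pain is not listed as an expected hyperthyroid symptom, handling it as an adverse event is reasonable, and new heart failure might well lead to withdrawal, which is stronger than a dose reduction.

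Much of this stands. It makes events unlikely and shows that investigators have the means to act. It does not set the action if chest pain occurs. The protocol explains the changed weight criterion but gives only the general titration rationale for leaving chest pain out.

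Stronger readings are tempting, and the documents do not support them:

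- *That heart failure has no cover for six months.* The sign criterion is open and carries no tolerability condition. Local results are also faxed to the research team, who can act on them.
- *That the sign criterion misses most monthly contacts.* Month 3 is the only scheduled in-person visit during 6-month treatment. Month 6 ends it, and telephone calls cannot detect most physical signs.
- *That risk rises in proportion to the longer exposure.* Exposure time is not a risk ratio, and the documents give no event rate.
- *That palpitations are missed on the calls.* The dose-reduction criteria already treat them as elicited there, so their absence from the telephone list is only wording.

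**Conclusion.** The concern holds for chest pain. As written, a tolerable episode reported from home requires no dose reduction in the 6-month phase and is left to clinical judgement. Heart failure is a secondary and narrower gap, limited to cases found outside the 3 month NIH visit.

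Severity is minor. Exclusion Criteria removes ischemic and structural heart disease, heart failure and arrhythmia. Study Implementation and Safety Testing require a baseline EKG and echocardiogram. Part 2 subjects have already been titrated as inpatients.

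The conclusion assumes that the 6-month list replaces the 2-week list, since no text carries the first one over. A reader might infer that subjects with chest pain would go untreated. The documents do not support that, because adverse events are recorded and investigators may act on them. The gap is in the rule.

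**What to change.** - Add chest pain and congestive heart failure to the 6-month dose-reduction criteria, without the intolerability condition and not limited to the 3 month NIH visit. Leave the action (reduce, hold or stop) to the investigators.
- Add chest pain, and breathlessness or swelling, to the telephone screen and to the items requested from the local physician at month 3.

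The cost is a short protocol amendment and a few questions at contacts already scheduled, with no extra visits or procedures. The downside is a few more non-specific symptom reports to review.

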### Glucose Management

Subjects who take insulin or insulin secretagogues may be at a small risk of hypoglycemia after initiation of thyroid hormone due to improvements in glucose disposal. Bedside blood glucose monitoring will be performed prior to meals and at bedtime (or more frequently if clinically indicated) in diabetic subjects. Insulin doses will be reduced on an as-needed basis to minimize hypoglycemia. Decision making regarding insulin dose reduction must be individualized for each patient based on clinical expertise, as patients with insulin receptor mutations may have fasting or postprandial hypoglycemia even in the absence of exogenous insulin treatment.

### Standardized Exercise

In order to maintain physical fitness during the hospitalization, sedentary subjects will engage in 30 minutes of walking on a treadmill each day (during both Periods 1 and 2) at a mild to moderate self-selected pace. In subjects who habitually exercise, the duration and intensity of exercise will be increased to be consistent with their typical exercise routine. This activity will be supervised by medical staff.

### Study Procedures

Short-term study:

| Study Day                | Off T3 |   |   |   | On T3 |   |   |   |   |   |   |   |   |    |    |    |    |    |    |   |
|--------------------------|--------|---|---|---|-------|---|---|---|---|---|---|---|---|----|----|----|----|----|----|---|
|                          | 0      | 1 | 2 | 3 | 1     | 2 | 3 | 4 | 5 | 6 | 7 | 8 | 9 | 10 | 11 | 12 | 13 | 14 | 15 |   |
| EKG & Echocardiogram     | X      |   |   |   |       |   |   |   |   |   |   |   |   |    |    |    |    |    |    |   |
| OGTT                     |        | X |   |   |       |   |   |   |   |   |   |   |   |    |    |    |    |    |    | X |
| Glucose & lipid turnover |        | X |   |   |       |   |   |   |   |   |   |   |   |    |    |    |    |    |    | X |
| Metabolic Chamber        |        |   | X |   |       |   |   |   |   |   |   |   |   |    |    |    |    | X  |    |   |
| DEXA (body composition)  |        |   | X |   |       |   |   |   |   |   |   |   |   |    |    |    |    | X  |    |   |
| DEXA (bone               |        |   | X |   |       |   |   |   |   |   |   |   |   |    |    |    |    |    |    |   |

|                               |   |   |   |   |   |   |   |   |   |   |   |   |   |   |   |   |   |   |   |
|-------------------------------|---|---|---|---|---|---|---|---|---|---|---|---|---|---|---|---|---|---|---|
| density)                      |   |   |   |   |   |   |   |   |   |   |   |   |   |   |   |   |   |   |   |
| PET-CT (age ≥ 18y)            |   |   |   | X |   |   |   |   |   |   |   |   |   |   |   |   |   | X |   |
| Adipose biopsy (age ≥ 18y)    |   |   |   | X |   |   |   |   |   |   |   |   |   |   |   |   |   |   | X |
| Muscle biopsy (age ≥ 18y)     |   |   |   | X |   |   |   |   |   |   |   |   |   |   |   |   |   |   | X |
| Continuous glucose monitoring |   |   | X | X |   |   |   |   |   |   |   |   |   |   |   |   | X | X |   |
| Temperature monitoring        |   |   | X |   |   |   |   |   |   |   |   |   |   |   |   |   | X |   |   |
| 7 point plasma glucose        |   |   | X | X |   |   |   |   |   |   |   |   |   |   |   |   | X | X |   |
| Bedside glucose monitoring    | X | X | X | X | X | X | X | X | X | X | X | X | X | X | X | X | X | X | X |
| Fasting research blood tests  | X |   |   | X | X |   |   |   |   |   | X | X |   |   |   |   |   | X | X |
| Thyroid function              | X |   |   |   | X | X | X | X | X | X | X | X |   | X |   | X |   | X | X |
| Food intake measurement       | X | X | X | X | X | X | X | X | X | X | X | X | X | X | X | X | X | X | X |
| BP & heart rate               | X | X | X | X | X | X | X | X | X | X | X | X | X | X | X | X | X | X | X |
| Body weight                   | X | X | X | X | X | X | X | X | X | X | X | X | X | X | X | X | X | X | X |
| Pregnancy test                | X |   |   |   |   |   |   |   |   |   |   |   |   |   |   | X |   |   |   |

Long-term study:

| Study Month                                     | 1 | 2 | 3 | 4 | 5 | 6 |
|--|----------|----------|----------|----------|----------|----------|
| Thyroid function (home labs)                           | X        | X        |          | X        | X        |          |
| Pregnancy test (females)                               | X        | X        | X        | X        | X        | X        |
| Telephone contact (safety)                             | X        | X        |          | X        | X        |          |
| NIH visit  |          |          | X        |          |          | X        |
| Pill count   |          |          | X        |          |          | X        |
| Fasting research blood tests                           |          |          | X        |          |          | X        |
| Thyroid function                                       |          |          | X        |          |          | X        |
| Vital signs (BP, heart rate, temperature, body weight) |          |          | X        |          |          | X        |
| Metabolic Chamber                                      |          |          |          |          |          | X        |
| DEXA (body composition)                                |          |          |          |          |          | X        |
| DEXA (bone density)                                    |          |          |          |          |          | X        |
| OGTT   |          |          |          |          |          | X        |
| PET-CT (age ≥ 18 years)                                |          |          |          |          |          | X        |
| Glucose & lipid turnover                               |          |          |          |          |          | X        |

|                            |  |  |  |  |  |   |
|----------------------------|--|--|--|--|--|---|
| Bedside glucose monitoring |  |  |  |  |  | X |
| Food intake measurement    |  |  |  |  |  | X |
| Echocardiogram             |  |  |  |  |  | X |

During the 6 month follow up period, safety labs will be obtained on a monthly basis, either locally near the subject’s home or at NIH. Safety labs will consist of trough T3 level, free T4, TSH, and pregnancy test (females). Monthly telephone assessments will be conducted during the months that no NIH visit is scheduled. This will include review of compliance, as well as screening for symptoms of hyperthyroidism, including changes in sleep, mood or behavior, school/work performance, tremulousness, anxiety, sweating, diarrhea, heat intolerance, and patient self-measurement of pulse rate and weight.

For those subjects where it is not feasible (due to distance from the NIH or inconvenience) for them to return to the NIH for a 3 month follow-up visit, the research team will communicate with the subject’s primary doctor (or endocrinologist) and see if they are willing to evaluate them. The local physicians would not be engaged in human subject research because they would be providing medical services that would typically be performed as part of routine clinical monitoring. The physician would be requested to obtain the following labs: thyroid function tests, fasting glucose, insulin, c-peptide, lipid panel, free fatty acids and high-sensitivity C-reactive protein. Research samples for storage would not be obtained as it would be difficult to ensure consistency in processing. Additionally the clinic visit would include vital signs, weight and a conversation about their medication compliance. All results would need to be faxed to the research team at the NIH.

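### The 6-month safety calls carry no hypoglycemia-specific question, and dose relief is written for insulin only, although the plan names secretagogue users as at risk too

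*Combined protocol and SAP*

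**What the plan says.** Glucose Management states the risk: "Subjects who take insulin or insulin secretagogues may be at a small risk of hypoglycemia after initiation of thyroid hormone". Its two safeguards are bedside glucose checks in diabetic subjects and dose adjustment: "Insulin doses will be reduced on an as-needed basis to minimize hypoglycemia". It leaves the decision to individual clinical judgment, because "patients with insulin receptor mutations may have fasting or postprandial hypoglycemia even in the absence of exogenous insulin treatment". The section is not restricted to the inpatient stay.

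For the 6-month study, the long-term table in Study Procedures places safety calls at months 1, 2, 4 and 5. The text below it gives their content: "This will include review of compliance, as well as screening for symptoms of hyperthyroidism". The symptom list ends with "tremulousness, anxiety, sweating, diarrhea, heat intolerance, and patient self-measurement of pulse rate and weight". Monthly safety labs are thyroid tests and, for females, a pregnancy test. If a subject cannot return to NIH at month 3, a local physician is asked for laboratory tests that include a fasting glucose, for vital signs and weight, and for "a conversation about their medication compliance".

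The 6-month dose-reduction criteria under Liothyronine (T3) begin with "Symptoms of thyroid hormone excess that are intolerable to the subject are reported by the patient, or elicited on monthly telephone screening", and one entry reads "Tremulousness, anxiety, sweating, diarrhea, or heat intolerance".

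Pre-study Medications keeps subjects on the drugs they were admitted with, names oral hypoglycemic agents among them, and excepts only insulin.

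**The concern.** A risk that the plan itself names should have a stated way of coming to light while subjects are at home. During the inpatient weeks it has one: daily bedside glucose. After discharge, the written call content does not ask whether the subject has had low glucose, what home readings show, or what doses of insulin or secretagogue are being taken. Those are the facts on which as-needed dose reduction would rest.

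Two consequences follow. First, if T3 works as hoped, insulin need may fall after discharge, when no contact is specified to ask about it. Second, a stable sulfonylurea user can enter, because the Exclusion Criteria bar only recent dose changes. That subject is named as at risk, yet the plan writes no dose relief for the drug.

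There is also a smaller risk of misattribution. Shakiness or sweating collected under a thyroid heading, with no prompt to think of glucose, could be answered by lowering T3 while the diabetes drug stays as it was.

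**Working it through.** The plan states no figure to reproduce. The check is a count and a comparison of sections.

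**1. Items on the calls** (Study Procedures, text below the long-term table)
- Compliance: 1.
- Symptoms: sleep, mood or behavior, school or work performance, tremulousness, anxiety, sweating, diarrhea, heat intolerance: 8.
- Self-measured pulse and weight: 2.
- Total: 1 + 8 + 2 = 11. Items on hypoglycemia, glucose or diabetes-drug dose: 0.
- Symptoms that can also reflect low glucose (tremulousness, anxiety, sweating; a clinical assumption, not a statement in the plan): 3 of 8.

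**2. Other sources of glucose or dose information after discharge**

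| Source | What it gives |
|---|---|
| Monthly safety labs | No glucose |
| Bedside glucose row, long-term table | Month 6 only |
| Month-3 NIH visit | Fasting glucose; planned as inpatient (Safety Testing; 2 days in the compensation table), so the general bedside rule could apply although the row is not marked |
| Month-3 local visit | Fasting glucose; no hypoglycemia or dose question |
| Adverse event section | Records events observed by or reported to the team |
| Outcome Measures | Total daily insulin dose is a 6-month secondary outcome; no collection time given |

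A single fasting value does not show episodes since the last contact.

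**3. Length of the first interval**
- One month = 365.25 / 12 = 30.44 days; three months = 91.3 days.
- Counted from discharge, month 3 falls 91 days later.
- Counted from T3 Day 1 with discharge on Day 15 (14 days later), it falls 91.3 − 14 = 77.3 days after discharge.
- So about 77 to 91 days, with two calls (months 1 and 2) in between. The monitored full-dose inpatient period is Days 3 to 14, which is 12 days.

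**4. How far entry A1c reassures**
Entrants to the 6-month study have A1c of at least 7%. The Sample Size Justification uses a fall of about 2.1 points, from a different intervention. As illustration only, a subject entering at 7 to 8% with that fall would reach 7 − 2.1 = 4.9% to 8 − 2.1 = 5.9%. High entry A1c is therefore reassuring at the start, but less so if the treatment succeeds. A1c is a mean measure, so this does not give a hypoglycemia rate.

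**5. The medication rules side by side**
- At risk (Glucose Management): insulin users and secretagogue users.
- Exempt from continuing unchanged (Pre-study Medications): insulin.
- Reduced as needed (Glucose Management): insulin.

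Secretagogues appear in the first line only.

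**The case against.** The strongest reply is that the plan is less bare than this suggests, and much of that reply stands.

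- The calls actively elicit tremulousness, anxiety and sweating. A reader might infer that, between discharge and month 3, hypoglycemia could surface only if a subject volunteered it. The documents do not support that. What is missing is a hypoglycemia-specific prompt.
- The wording of the call content is not a closed list, and an investigator may well ask about glucose anyway.
- A reader might infer that insulin dose is not planned as data. It is a 6-month secondary outcome; only the timing of its collection is unstated.
- The T3 reduction rule applies to symptoms of thyroid hormone excess. Shakiness recognized as hypoglycemia does not meet it, and nothing there prevents an insulin reduction as well. If T3 is driving the hypoglycemia, lowering it also removes a cause.
- Pre-study Medications describes background therapy. A reader might take it as forbidding a sulfonylurea reduction for an adverse event, but it does not say so. The gap is that no reduction is provided for, and the documents do not say how many patients take a secretagogue.
- The population is extremely insulin resistant. In the motivating case A1c fell from 9.9 to 5.6% over 3 years with all diabetes drugs stopped. That was one patient on T4, with negligible insulin-stimulated disposal before and after, and the plan's account mentions no hypoglycemia. It is thin evidence about an interval of 77 to 91 days.

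These points lower the weight. None of them supplies a specific question on the calls or a written rule for secretagogues.

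**Conclusion.** The point holds as a minor safety-monitoring gap with a cheap remedy. Followed as written, the four calls and the local month-3 visit contain no hypoglycemia question and no insulin or secretagogue dose question, and the as-needed reduction omits one of the two groups named as at risk. Confidence is high for what the text contains and omits, and low for the consequences. The plan calls the risk small and gives neither an event rate nor a count of secretagogue users, so missed episodes cannot be estimated. Sample size and the primary analysis are not affected.

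It would be tempting to conclude that T3 should not be lowered for these symptoms until a glucose reading is in hand. That goes too far. A reading taken on a monthly call says nothing about glucose during an earlier symptom, the documents do not say whether subjects have meters, and such a condition could delay a safety action.

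The misattribution concern rests on the clinical assumption that the three named symptoms can accompany low glucose. It is a possibility, not a demonstrated failure of the rule.

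**What to change.** 1. **Calls at months 1, 2, 4 and 5, and the month-3 visit (NIH or local).** Ask about hypoglycemic episodes since the last contact, any home glucose readings available, and current insulin and secretagogue doses. State that the NIH team reviews the answers for the individualized decision described in Glucose Management.
2. **Pre-study Medications and Glucose Management.** Extend the insulin exception and the as-needed reduction to secretagogues when the reason is hypoglycemia, and record each change.
3. **Liothyronine (T3), 6-month criteria.** When an insulin or secretagogue user reports tremulousness, anxiety or sweating, also ask about glucose readings taken at the time and consider hypoglycemia. Do not make a reading a precondition for reducing T3.

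The cost is a few minutes per contact, a small data form, and about one amended sentence in each of the four places. No visit or sample is added. A subject without a meter answers the episode and dose questions only. The dose question would also help document the insulin-dose outcome.

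The real trade-off is an occasional secretagogue change during a pre-post study with A1c as its endpoint. Insulin changes are already allowed, so this is a small extension; report such changes alongside the A1c result.
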